### **c Aim, objectives and Hypotheses:**

Aim and objectives:

The aim of this study is to evaluate the cost-effectiveness of the RAMP-HT of the HA in primary care patients with uncontrolled hypertension.

The objectives are to

1. Evaluate the long term (5-year) effectiveness of RAMP-HT compared to usual care in reducing cardiovascular complications, end-stage renal disease and all-cause mortalities in a cohort of primary care patients with uncontrolled hypertension at baseline
2. Estimate the direct medical cost of RAMP-HT and other health services

among primary care HT patients with or without complications

3. Evaluate the cost-effectiveness of RAMP-HT, compared to usual care, in gaining one Quality-Adjusted Life Year (QALY) in primary care patients with uncontrolled hypertension

Hypotheses:

1. RAMP-HT is more effective in reducing 5-year cardiovascular complications, end stage renal disease and all-cause mortality among primary care patients with uncontrolled hypertension compared to usual care
2. The direct medical cost of RAMP-HT patients, for the same disease complication status, is not higher than that of usual care except for the RAMP-HT cost
3. The direct medical cost of HT patients with one or more complications is higher than that of HT patients without any complication
4. RAMP-HT is cost-effective compared to usual care, i.e. the incremental cost-effectiveness ratio (ICER) per QALY gained is below the threshold value of 1 annual GDP (Gross Domestic Product) per capita of Hong Kong (HK\$295,303, 2013), which is the benchmark recommended by the World Health Organization

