#### *Sample size calculation*

- a. For the long-term effectiveness evaluation, the difference in 5-year incidence of CVD between the RAMP-HT and usual care group is the primary outcome. From the result of our RAMP-HT QOC study, the observed 1-year incidence of CVD in the RAMP-HT and usual care group was 1.33% and 1.76% respectively. A conservative estimate of the 5-year incidence of CVD in RAMP-HT and usual care group would be 7% and 8%, respectively. A minimum sample size of 7,116 subjects from each group will be needed to detect a difference of 1% in incidence rates of CVD between RAMP-HT and usual care group with 90% power and at 5% level of significance.

We have identified from the HA CMS data set of the RAMP-HT QOC study 8,681 eligible RAMP-HT patients and 8,681 usual care patients who fulfilled the inclusion criteria and without any exclusion criterion matched by propensity score matching. These two matched cohorts will be the subjects of this long-term effectiveness and cost-effectiveness

study. The flow chart of subject selection is attached in Appendix C.

- b. For the costing analysis, 140 subjects from each of the RAMP-HT and usual care groups will be required to show that the direct medical costs of RAMP-HT patients (excluding RAMP cost) is not higher than that of usual care HT patients by independent one side t-test with 0.3 effect size and 80% power at 5% significance level.

307 RAMP-HT and 291 usual care patients had been recruited from May 2013 to March 2014 in GOPCs across Hong Kong for the longitudinal evaluation of patient reported outcomes (PRO) in the RAMP-HT QOC study. These patients will be follow-up from May 2015 to March 2016 as part of our RAMP-HT QOC study; telephone survey on private health service utilization will be conducted at the same time. Taking 25% attrition rate into account, 230 RAMP-HT and 218 usual care patients will complete the questionnaire. This sample will be adequate for the comparison of private medical cost between RAMP-HT and usual care group.

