#### *(ii) Direct Medical Costs of HT patients*

The medical cost analysis will focus on the direct medical costs involved in the care of HT patients without or with specific HT complications (i.e. CHD, heart failure, stroke and ESRD) in both public and private healthcare sectors; indirect cost (e.g. opportunity cost) and non-medical costs (e.g. transportation cost, carer cost) will not be measured.

Public medical costs will be estimated from products of the unit costs (published in the HKSAR Government Gazette and Hospital Authority ordinance (Chapter 113) of charges for non-entitled persons) and the utilization rates of 1) dispensed drugs (*note: self-financed drugs will be considered as private medical cost, see below*), 2) laboratory tests and investigations, 3) healthcare services including general outpatient clinics (GOPC), specialist outpatient clinics (SOPC), allied health services (e.g. dietician, physiotherapist or occupational therapist), accident and emergency (A&E) department and 4) admissions to hospital in the 12 months before baseline and at 12, 24, 36, 48 and 60 months after study enrolment for each patient in the study cohorts. The data extraction will be carried out by the HA statistics team.

Private direct medical costs include the cost of all private Western doctor and Chinese medicine practitioner consultations, private hospitalisation and self-medications inclusive of self-financed medications prescribed by the HA. 598 HT patients (307 RAMP-HT patients and 291 usual care patients) who were recruited from HA GOPCs for the longitudinal evaluation of patient reported outcomes (PRO) in the evaluation of QOC RAMP-HT study from May 2013 to March 2014 will be invited to complete a “private medical cost of HT questionnaire” (Appendix E) by telephone. The questionnaire is adapted from the costing questionnaire that was used in our in-depth study on the cost-effectiveness analysis of RAMP-DM that had proven feasibility and validity (HHSRF # EPC\_HKU-1A).

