### **Cost Analysis of RAMP-HT**

Descriptive statistics will be used to summarize the costs of RAMP-HT and annual direct medical costs for RAMP-HT and usual care patients at baseline and over each of 5 subsequent years, overall, and by the presence of complications. The cost of each healthcare service will be derived by multiplication of the unit cost from Gazette and Hospital Authority ordinance and the number of respective services used by the patients. To avoid double counting the cost of drugs and laboratory tests, the Government Gazette cost of each GOPC and SOPC attendance will be adjusted by a factor of 0.7 to include only the manpower cost. The total public medical costs will be calculated by summing up all costs of drugs, laboratory tests and each healthcare service utilisation. The private medical costs will be estimated by summarizing the self-reported costs of private consultations, self-medication and private hospitalisation. The average annual public and private direct medical costs per patient will be analysed by HT complication status (CHD, heart failure, stroke and ESRD), and by RAMP-HT and usual care HT groups. To determine whether the direct medical costs of the RAMP-HT cohort is higher than the usual care HT cohort, one sided independent t-test will be performed.

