### **Health Preference by HT Complication Status**

The SF-6D preference will be calculated by the HK population specific

algorithm^15 by HT complication status. Independent t-test will be used to compare the SF-6D values of HT patients with each complication to those without any complication, and between RAMP-HT and usual care HT patients.

All above statistical analyses will be performed using STATA Version 13.0 (StataCorp LP. College Station, Texas, U.S.). All significance tests will be two-tailed and those with a p-value less than 0.05 will be considered statistically significant.

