3. HT patients with complications may die from either HT-related death or other cause of death.
4. RAMP-HT is effective in reducing HT complications for a period of 5 year; thus the transition probability adjustment of CVD/ESRD development (as determined by the annualized hazard ratio obtained from our long-term effectiveness analysis) will be applied to the model of the RAMP-HT cohort in the first five years. After 5 years, the RAMP-HT will have the same transition probabilities of developing HT complications as usual care HT cohort.
5. RAMP-HT is repeated every 12-24 months and the effectiveness of RAMP-HT will not decrease over time; thus the 5-year effect of RAMP-HT can be annualized. Adjustment will be made on the average duration of repeat RAMP-HT based on available empirical data in order to avoid over-estimation of the RAMP-HT cost.
6. The medical cost (public and private) of HT patients in usual care and RAMP-HT programme is the same for the same HT health status except for the additional RAMP-HT cost.
7. All costs and health preference will be discounted by an annual rate of 3.5% as recommended by the guidance of National Institute for Health and Clinical Excellence (National Institute for Clinical Excellence 2008).

[Word Count: 3968 ]

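### The cost hypothesis is that RAMP-HT is not higher than usual care, but the planned test asks whether it is higher, with no margin or decision rule and a conflicting two-tailed convention

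*Combined protocol and SAP*

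**What the plan says.** Four places in the combined protocol and SAP bear on the same comparison.

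- **Section c, Hypothesis 2:** under RAMP-HT, direct medical cost, "for the same disease complication status, is not higher than that of usual care except for the RAMP-HT cost".
- **Sample size calculation, item b:** 140 patients per group are needed to show that direct medical cost, programme cost excluded, "is not higher than that of usual care HT patients by independent one side t-test with 0.3 effect size", with 80% power at the 5% level. The expected survey completers are 230 RAMP-HT and 218 usual care. Of these the section says: "This sample will be adequate for the comparison of private medical cost between RAMP-HT and usual care group".
- **Cost Analysis of RAMP-HT:** average annual costs are analysed by "HT complication status (CHD, heart failure, stroke and ESRD), and by RAMP-HT and usual care HT groups". The test is then specified, asking "whether the direct medical costs of the RAMP-HT cohort is higher than the usual care HT cohort, one sided independent t-test will be performed", with no margin named.
- **Health Preference by HT Complication Status**, closing paragraph, which refers to all the analyses above it: "All significance tests will be two-tailed and those with a p-value less than 0.05 will be considered statistically significant".

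Outcome Measures lists direct medical cost, by group and complication status, among the primary outcomes.

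**The concern.** A one-sided test of whether cost is higher puts the burden of proof on showing an excess. Rejection counts against Hypothesis 2. Non-rejection leaves the question open, because a real excess may have gone undetected. Showing that cost is not higher needs the opposite construction: a largest tolerable excess, and an upper confidence bound below it. The plan gives neither.

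The test sentence also leaves out two conditions attached elsewhere: exclusion of the programme cost (Hypothesis 2 and the sample size) and comparison at the same complication status (Hypothesis 2). Finally, the general two-tailed rule has no exception for a test that two other sections make one-sided.

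What is at stake is the conclusion on a stated hypothesis about a primary outcome. As written, the plan does not prevent a non-significant result from being taken as support.

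**Working it through.** **Inputs.** From the sample-size section: effect size 0.3, one-sided 5%, 80% power, 140 per group; 307 and 291 recruited with 25% attrition, so 307 × 0.75 ≈ 230 and 291 × 0.75 ≈ 218. The documents give no cost SD, so everything is in SD units, with equal SDs assumed. The true excesses of 0.1 and 0.2 SD are illustrative assumptions.

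**1. Reproducing the stated size.** n per group = 2(z₁₋α + z₁₋β)² / 0.3².

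- One-sided 5%: 2(1.645 + 0.842)² / 0.09 ≈ 137.4, so 138 (139 by exact t). This agrees with the stated 140.
- Two-sided 5%: 2(1.960 + 0.842)² / 0.09 ≈ 174.4, so 175 (176 by exact t). This does not.
- Non-inferiority with a 0.3 SD margin, no true difference and one-sided 5%: the same formula, so again 138.

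The stated size is therefore one-sided. It cannot show whether 0.3 is a difference to detect or a margin.

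**2. What the test of higher can miss at 230/218.** SE = √(1/230 + 1/218) = 0.0945 SD. P(non-significant | true excess d) ≈ Φ(1.645 − d/0.0945).

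| True excess | Argument of Φ | Missed (noncentral t) |
|---|---|---|
| 0.1 SD | 1.645 − 1.058 = 0.587 | 72% |
| 0.2 SD | 1.645 − 2.116 = −0.471 | 32% |
| 0.3 SD | 1.645 − 3.174 = −1.529 | 6% |

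**3. What a non-significant result leaves open.** The critical observed difference is about 1.648 × 0.0945 = 0.156 SD. The one-sided 95% upper bound is the observed difference plus 0.156 SD.

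- Observed difference at the critical value (worst case): 0.156 + 0.156 ≈ 0.31 SD is not excluded.
- Observed difference of zero: about 0.16 SD is not excluded.

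**4. Sidedness.** Two-sided power at 0.3 SD, exact t:

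- 140 per group: SE = √(2/140) = 0.1195; Φ(0.3/0.1195 − 1.960) = Φ(0.550), 71%.
- 230/218: Φ(3.174 − 1.960) = Φ(1.214), 89%.

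**5. What a margin rule would demand at 230/218 if true costs are equal.** P(upper bound < m) ≈ Φ(m/0.0945 − 1.645).

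- m = 0.2 SD: Φ(0.471), 68%.
- m = 0.3 SD: Φ(1.529), 94%.

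**The case against.** The strongest reply is that this is a non-inferiority test that was never labelled. The sample-size section describes a one-sided test meant to show not higher, the 140 per group fits a 0.3 SD margin, and the analysis section names no null or alternative hypothesis. This may well be what was intended. But the 0.3 is called an effect size, has no HK$ value and is absent from the analysis section. If it is a margin, the test sentence asks the wrong question; if it is not, there is no margin. The text needs changing either way.

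It is also fair to say that the practical gap in the private-cost survey is small. The test of higher is non-significant below an observed 0.156 SD, and a 0.3 SD margin would be met below 0.3 − 0.156 = 0.144 SD. That closeness depends on 0.3 SD being an acceptable excess, which nobody has argued. The plan also nowhere says that a non-significant result will be reported as support; the defect is that it gives no rule for reaching that conclusion.

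On the omitted conditions, the sentence before the test does mention analysis by complication status and group, so the author may have meant them to carry over. They should be stated. On sidedness, a specific instruction would ordinarily override a general convention, so one clause settles it.

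A reader might infer more than the documents support:

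- **That the two readings give opposite verdicts on public costs at 8,681 per arm.** This requires applying the 0.3 effect size to the full cohorts, which no section does.
- **That the cost test undermines the ICER.** Under the Markov assumptions, "The medical cost (public and private) of HT patients in usual care and RAMP-HT programme is the same for the same HT health status", apart from the programme cost. That is a disclosed simplification, and the test result does not enter the model. An alternative model run is a matter of preference and is not asked for here.

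**Conclusion.** The point holds as an inconsistency between hypothesis, sample size, analysis and testing convention. Carried out as written, the planned test cannot establish Hypothesis 2. In the private-cost survey it would miss a true excess of 0.2 SD about one time in three, and a non-significant result could leave up to about 0.31 SD unexcluded, though that is the extreme case and about 0.16 SD applies when the observed difference is zero.

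The sample-size arithmetic is correct, and it would be wrong to infer that the survey is underpowered: the expected completers exceed the planned 80% power at 0.3 SD whether the test is one-sided (94%) or two-tailed (89%).

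These figures assume 25% attrition, equal SDs and sample means close enough to normal for a t-test on costs. What the SD amounts to in HK$ cannot be judged from the documents. This should be corrected, and it can be done in the text.

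**What to change.** 1. **Align the hypothesis, sample size, analysis and testing convention.** Report the mean cost difference, RAMP-HT minus usual care, with its confidence interval. Exclude the programme cost, and present the difference by complication status or adjusted for it. State that this conditions on an event after baseline.
2. **State the decision rule.** Conclude not higher only if the one-sided 95% upper bound is below a margin fixed before costs are compared by arm, which the Timeline places in December 2016 to March 2017. If 0.3 SD is that margin, say so, justify it in HK$, and state whether it covers public as well as private costs. Say explicitly that a non-significant test of higher does not support Hypothesis 2.
3. **Name this test as the exception to the two-tailed rule.**
4. **For public costs, adjust for baseline spending.** Public utilisation is already to be extracted "in the 12 months before baseline and at 12, 24, 36, 48 and 60 months after study enrolment for each patient", so the pre-baseline year is available.

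The cost is wording in four sections and one regression, with no new data. The real price is that not higher becomes harder to conclude for private costs if the margin is tighter than 0.3 SD: with equal true costs at 230/218, the chance of meeting it falls from 94% at 0.3 SD to 68% at 0.2 SD.

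### Arm comparisons of cost and SF-6D are covariate-free t-tests: prior public cost is collected but not used in the test, and no matching is described for the survey sample behind private cost and SF-6D

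*Combined protocol and SAP*

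**What the plan says.** All references are to the combined protocol and SAP.

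- **Cost test.** Section d(v), Cost Analysis of RAMP-HT, states that to judge whether the RAMP-HT cohort costs more, a "one sided independent t-test will be performed". No covariate, regression or weighting is named. Baseline cost appears there only among the descriptive summaries. Direct medical cost is listed as a primary outcome in d(iii).
- **SF-6D test.** Health Preference by HT Complication Status states: "Independent t-test will be used to compare the SF-6D values" by complication, "and between RAMP-HT and usual care HT patients". Again no covariates are named.
- **What is collected.** Direct Medical Costs of HT patients plans to extract public utilisation "in the 12 months before baseline and at 12, 24, 36, 48 and 60 months after study enrolment for each patient" in the study cohorts.
- **What is matched.** Baseline Covariates lists demographics, co-morbidities, clinical parameters and treatments. Prior cost or utilisation is not among them.
- **Survey sample.** Sample size calculation, item b, takes private cost from 307 RAMP-HT and 291 usual care patients who "had been recruited from May 2013 to March 2014 in GOPCs across Hong Kong". The data-source table takes SF-6D from 410 and 388 patients surveyed over the same dates. No matching is described for either. The matched cohort consists of RAMP-HT enrolees from October 2011 to March 2012 and usual care patients drawn from the clinical management system.
- **Contrast.** The Cox models in Long Term Effectiveness of RAMP-HT adjust for all baseline covariates.

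**The concern.** This is a non-randomised comparison. For clinical events the plan matches and then adjusts again in the Cox models. For cost and utility it stops at a t-test, and the protection left differs by data source.

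Public cost is protected by the matching, with two gaps. Prior cost, a natural predictor of later cost, is neither matched on nor used in the test. Hypothesis 2 concerns cost at the same complication status. Patients with complications at baseline are excluded, so that status arises during follow-up, and pairs matched at baseline do not stay together within it.

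For private cost and SF-6D the documents describe no protection at all. The sample has its own recruitment window and source.

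An imbalance could push either way. It could make RAMP-HT look costlier than it is. It could also hide a real excess, and a non-significant test for higher cost would then be read as support for hypothesis 2 and for model assumption 6 (equal cost by health state across arms).

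**Working it through.** **1. The plan's own figure.** The plan states that "140 subjects from each of the RAMP-HT and usual care groups will be required", "by independent one side t-test with 0.3 effect size and 80% power at 5% significance level". With n = 2(z_0.95 + z_0.80)²/d² = 2(1.645 + 0.842)²/0.3² = 137.4, this gives 138 per group; the exact t solution is 139. The stated 140 is reproduced. Expected completers are 307 × 0.75 = 230 and 291 × 0.75 = 218, which give 93.6% one-sided power at 0.3 SD. Sample size is not the problem.

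**2. Precision in the full public-cost cohort.** With 8,681 per arm, the SE in SD units is √(2/8,681) = 0.0152. The detectable difference at one-sided 5% and 80% power is 2.486 × 0.0152 = 0.038 SD. Adjusting for a baseline cost with correlation r (assumed) multiplies this by √(1 − r²):

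| r (assumed) | Variance reduction r² | Detectable difference |
|---|---|---|
| 0 | 0% | 0.038 SD |
| 0.3 | 9% | 0.036 SD |
| 0.6 | 36% | 0.030 SD |

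The planned effect is 0.3 SD, so this gain hardly matters.

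**3. Bias in the full public-cost cohort.** If there is no true difference but the RAMP-HT arm is costlier by b SD through residual imbalance, P(reject) = 1 − Φ(1.645 − b/SE). For an assumed b = 0.05, b/SE = 3.29 and P(reject) is about 95%. At this size a small uncorrected imbalance decides the test.

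**4. Complication strata.** The planning incidences of 7% and 8% give about 8,681 × 0.07 = 608 and 8,681 × 0.08 = 694 patients with CVD. The two groups differ in number, so they cannot be a set of complete matched pairs. Balance within them has to be checked or modelled; it does not follow from the matching.

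**5. Private cost in the survey sample.** SE = √(1/230 + 1/218) = 0.0945. All imbalances are assumed.

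| Imbalance b (assumed) | b/SE | One-sided error, nominal 5% |
|---|---|---|
| 0.05 SD | 0.53 | 13% |
| 0.10 SD | 1.06 | 28% |
| 0.20 SD | 2.12 | 68% |

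In the other direction, a true 0.3 SD excess masked by 0.1 SD leaves 0.2/0.0945 = 2.12, so power is about 68% instead of 94%. Masked by 0.2 SD, power is about 28%.

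**6. SF-6D.** SE = √(1/410 + 1/388) = 0.0708. For an assumed b = 0.1, b/SE = 1.41 and the two-sided error is about 29% instead of 5%.

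**7. Route to the ICER.** The Markov model takes average cost and preference values per disease state, and assumption 6 sets cost equal across arms within a state apart from the programme cost. The model sections use neither arm contrast as an input.

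**The case against.** The strongest reply concerns public cost. Those cohorts are matched one to one with a calliper of 0.001 on age, sex, smoking, social assistance, co-morbidities, blood pressure, lipids, BMI and drugs. The comparison is therefore adjusted by design, and the planned baseline summaries would show an imbalance in prior cost. This stands: a reader might infer that public cost is compared with no control for confounding, and the documents do not support that. What remains is prior cost and balance within complication strata. A descriptive table can show an imbalance, but it does not correct the test.

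A reader might also infer that the survey sample is known to be unmatched and confounded. The documents do not show this. The sample belongs to a separate quality-of-care study whose protocol is not included, and no imbalance is reported. The supportable statement is that no matching is described and confounding is possible.

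Nor should precision be presented as the case for change; step 2 shows that it is ample.

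Two further points stand. The contrast with effectiveness is only partial: that section also uses unadjusted tests and takes the number needed to treat from unadjusted rates, and only the Cox models adjust. The survey fix may also be hard to carry out, because pre-baseline cost is described only for the study cohorts, the extract is anonymous, and no linkage to the telephone sample is described.

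**Conclusion.** The point holds in a limited form. The arm tests for a primary cost outcome and for SF-6D name no covariates. For public cost, an already collected pre-baseline value is left out of both the matching and the test, and baseline matching does not guarantee balance within later complication status. For private cost and SF-6D, no protection against confounding is described.

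The size cannot be fixed from the documents, which give no cost SD, no correlation of prior with later cost and no survey imbalance. Under assumed imbalances of 0.05 to 0.20 SD, the one-sided 5% error for private cost runs from about 13% to 68%, and is about 28% at 0.1 SD. These figures show how sensitive the test is; they do not estimate the actual bias.

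A reader might infer that the ICER itself is biased. The documents do not support that, because the model works from state averages and assumes equal cost across arms. The consequence falls on hypothesis 2 and on how well assumption 6 is supported.

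**What to change.** **Public cost.** Replace the t-test by a regression of annual public cost on group, pre-baseline 12-month public cost and the covariates listed under Baseline Covariates, overall and within complication status. Report the adjusted mean difference with a robust or bootstrap confidence interval. A GLM for skewed cost is optional. The data are already in the extraction plan, so this costs revised wording and slightly more analysis.

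**Private cost and SF-6D.** State how the survey patients were selected in each arm and which baseline covariates exist for them. Adjust the arm contrasts for those covariates. If none can be obtained or linked, report the contrasts as descriptive only and do not use them as a test of hypothesis 2. This may need linkage work, which the plan does not yet describe.

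**Model.** Say in the plan that the adjusted comparison is the evidence offered for assumption 6.
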